Effects of Lactoferrin on Chronic Inflammation in the Elderly (ELCIE)

NCT number: **NCT02968992**

12/15/2017

Date: December 15, 2017
Principal Investigator: [name].
Application Number: IRB_00094982

JHM IRB - eForm A – Protocol

1. Abstract

Mild persistent activation of inflammatory pathways, often termed chronic inflammation (CI) is observed in up to 30% of older adults (1;2). Dozens of population studies have identified significant associations between serum-based pro-inflammatory measures and functional decline, frailty, worsening chronic illness, cognitive decline, mortality and reduced gait speed (2). Serum markers of CI such as interleukin 6 (IL6) and soluble TNF-alpha receptor 1 (sTNFR1) are increasingly recognized as pathologic and in part causal in many of age-associated processes such as sarcopenia and neurodegeneration that in turn drive functional and cognitive decline and worsening chronic disease states in older adults (3;4). The etiology of the chronic elevation of these mediators in older adults is complex and includes chronic disease states, increased free radical production, senescent cells, altered microbiome, and decreased barrier function of GI epithelium (4-6). Despite the increased understanding of etiologies and consequences of CI in older adults, few options have been tested for reducing CI and associated adverse health outcomes. This is in part because of lack of specific biological targets and because of safety concerns regarding presently utilized anti-inflammatory drugs in older adults (7). In response, this research aims to test the effects of lactoferrin (recombinant human lactoferrin {rhLF}), a known anti-inflammatory agent, on reducing low grade CI, mobility limitations, and cognitive decline in older adults.

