Most prior studies linking CI to adverse health in older adults have relied on single serum-based biomarkers such as IL6 or C-reactive protein (CRP). Studies have emerged that demonstrate that elevations in ≥2 inflammatory markers are more strongly associated with adverse outcomes (53-57). Approaches to aggregate markers can be categorized into “unsupervised” and “supervised”, with unsupervised aggregation being a summary of markers obtained based only on their joint distribution, e.g. by z-scores, principal component analysis or exploratory factor analysis (58;60) and supervised aggregation also considering biological understanding, or externally validating response (e.g., mortality(26)) for an “optimally” predicting response. Our group has made key contributions to work on supervised aggregation of inflammatory markers; including the first study applying latent variable (LV) modeling to summarize markers in accordance with biology understanding (61). Subsequently, we demonstrated that an inflammatory index (IIS) combining serum levels of IL6 and sTNFR1 provided superior prediction of 10-year mortality in the Cardiovascular Health Study (N=5,177) (26) over many other cytokines. As rationale for the use of these measures for diagnosis of CI in this project over other markers, we performed additional analyses (table 1) using the likelihood ratio test that shows that IL-6, TNFR1, and combined measure IIS are superior predictors of gait speed declines over 10 years when compared to CRP and interleukin 1 receptor antagonist (IL1RA). The cutoff

point for the study inclusion criteria for IL6 was identified based on a published threshold serum value above which adverse outcomes are much more common; the value for sTNFR1 was identified using a loess curve generated from data analyzed from the Cardiovascular Health Study (17;18;26). This background research provides strong rationale for the use of these measures to identify CI and to monitor treatment efficacy of lactoferrin on CI.

4. Study Procedures

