Baseline Visit (BV): Individuals meeting eligibility criteria (described below) will be scheduled for a baseline visit. This visit will consist of a brief medical history review and blood draw, along with outcome measurements described thoroughly below. At the end of the visit, the pharmacy or site coordinator will distribute the randomized study product with instructions. A structured walking program and encouragement of physical activity for participants in all treatment arms will be included. Participants will also receive an accelerometer for home mobility measurement along with detailed instructions for use.

Follow up visit (FUV): Monthly in person visits will take place, with telephone contact every two weeks by study staff between visits to help maintain adherence and assess for adverse effects. Pill counts and side effect assessments will take place at FU1, FU2, and FU3. FU6 will include measures checked in Table 2 and described below.

Table 2

	PSC	SV	ABT	BV	FU1	FU2	FU3			FU6.
Phone Screen	X									
Medical History		X								
Brief Medical History Review				X	X	X	X			X
Informed Consent		X								
Demographics		X								
Randomization				X						
Frailty Assessment				X			X			X
Activity Assessment				X			X			X
Vital Signs (BP, HR, Hgt,Wgt. Temp, Resp.)		X	X	X	X	X	X			X
Short Physical Performance Battery				X			X			X
Side Effect Assessment					X	X	X			
4 meter walk		X		X			X			X
Six-minute walk test				X			X			X
Blood Draw		X	X	X	X		X			X
Physical Exam		X								
MMSE		X								
Cognitive measures (Trail Making Test and Digit Symbol Substitution Test)				X			X			X
Accelerometry				X			X			X
Pill Calendar				Marked Daily to end of Month 3						
Abbreviations: PSC: Prescreening contact; SV: Screening visit; ABT Additional Blood test (to further determine eligibility for those whose cytokine levels are above threshold); BV: Baseline visit; FU1-6: Follow up months 1-6 of pilot study										

All laboratory results will be reviewed by study physicians during the study and there will be frequent review

of adverse and/or other unexpected events. Following study protocol, all adverse events will be reported to the IRB and National Institute on Aging (NIA) as per requirements. Participants will be able to report issues at study contacts but will also be provided with a number to call ad hoc as needed if issues related to study participation arise. If participants choose to withdraw from the study, their medical care will not be affected in any way.

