Measurements Performed at Visits:

Phlebotomy (primary outcome measure): Primary outcome will be serum IL-6 and sTNFR1 as measured by ELISA as previously performed in the PI's laboratory by an experienced laboratory technician. Blood will also be measured for CBC w/Diff, and CMP, these measures will be made from blood drawn at SV, ABT, BV, FU1, FU3 and FU6. Rationale for the choice of these measures are provided above in the background section.

A Physical Exam will be taken at SV. A Medical History will be taken at SV and a Brief Medical History Review at BV and all subsequent FUV. These are to assess eligibility or contraindicate the intervention, detect new conditions or complications and other safety signals, and to measure important covariates (i.e. demographics, past medical history, current activity levels, routine medication, and vitamin use).

4 meter walk: Speed of walking at usual pace over 4 meters will be measured at the SV, BV, FU3, and FU6.

Six-minute walk: This is performed at the BV, FU3, and FU6 by having the participant walk along a straight hallway for six minutes and measuring the distance walked and the sensation of leg fatigue and dyspnea. The participant is given scripted prompts at one-minute intervals, but the test is largely self-directed and self-limited.

Short Physical Performance Battery (SPPB): This is an assessment of lower extremity functioning comprised of gait speed, balance, and leg strength and is performed at the BV and FU6. As part of the SPPB, participants will complete a balance test assessing their ability to stand without assistance and a chair stand test.

Cognitive Function Measures: The Digit Symbol Substitution Test (DSST) is a sensitive measure in cognitively normal older adults. It measures attentional control and switching, and more broadly executive processes and thus is not sensitive to impairment in particular brain regions. It is a highly precise measure across the range from cognitively normal to mildly impaired older adults and takes about 90 seconds to administer (75). The DSST will be conducted at BV, FU3, and FU6. The Trail Making A and B Test measures executive functioning and task-switching, is highly sensitive to change and takes 5-10 minutes to administer (76). This test will be performed at BV, FU3, and FU6. An MMSE (a mini-mental state exam) will also be performed at the BV.

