Side Effect Assessment: A Side Effect Assessment will be conducted at FU1, FU2, and FU3. The purpose of this assessment is to monitor participants' responses to lactoferrin and to assess for any adverse side effects.

Activity Assessment: Participants will answer questions about their physical activity and energy levels. This assessment is conducted at BV, FU3, and FU6.

Frailty Assessment: This assessment is completed at BV, FU3, and FU6. This assessment measures participants' walking speed and grip strength, and includes questions about weight loss.

Vital Signs: Participants' vital signs will be measured at every study visit. These measurements include height, weight, blood pressure, respiratory rate, and temperature.

Additional Physical and Functional Measurements:

Home Mobility Measurement: An Acti-Graph® Link Activity monitor will be placed on the participant's non-dominant wrist at the end of the BV. This model includes an ambient light designed to provide environmental information and a gyroscope and magnetometer to capture position and rotational data. Accelerometry counts will be measured at a sampling frequency of 80 hertz for 7 days immediately

after completing the BV, 3-month, and 6-month visits. Participants will be asked to wear the device at all times except when swimming for >30 minutes. Monitors will be mailed via pre-addressed express mail packets where all raw data will be downloaded using commercial software (ACTLIFE, v6) to derive activity data in g force and counts/min. The JHU Statistical Methods for Applications and Research in Technology ("SMART"-stats) group, developers of the "movelets" technology that enables the use of raw data (62), will use collected data to: (i) characterize cumulative daily activity, (ii) assess daily circadian patterns of activity, (iii) assess physical activity variability, (iv) model patterns of daily activity, and (iv) estimate walking speed (62, 63, 64). These measurements greatly extend what is normally available from accelerometers and will complement mobility measures by describing function enacted in daily life.

5. Inclusion/Exclusion Criteria

Inclusion: Age 70 and older; able to complete 4- meter timed walk; walking speed ≤ 1.0 m/sec; serum IL-6 level ≥ 2.5 pg/ml or TNFR1 level ≥ 1500 pg/ml. Consistent with NIH guidelines, both genders and minority persons are enrolled. Participants will be followed for 6 months to investigate the effects of the treatments on gait speed and other outcomes.

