Exclusion criteria: Participants with IL-6 levels above 30.0 pg /ul. Daily anti-inflammatory drug use (prednisone, Advil, Aleve, Remicade, Enbrel, methotrexate, standing NSAID, aspirin greater than 325 mg per day), lower extremity mobility disability caused by Parkinson's disease, CVA with residual motor deficit, severe osteo or rheumatoid arthritis, symptomatic claudication, hospitalization within 3 months for MI, angina, infection requiring antibiotics, or joint replacement, and for other reasons that markers may be elevated such as active or chronic malignancies MMSE < 21.

6. Drugs/ Substances/ Devices

Lactoferrin is a basic glycoprotein initially identified in milk but subsequently identified in most exocrine secretions and in granules secreted from neutrophils (8). It has pleiotropic anti-inflammatory effects that range from the coating and degradation of invading organisms and their antigenic cellular components, to the sequestration of free iron needed by invading organisms to thrive, to the suppression of inflammatory (NFkB) signaling, and the modulation of the adaptive immune system (8-10;12). A recent study that characterized a lactoferrin knock out mouse demonstrated a colonic inflammatory phenotype which suggests an important role for lactoferrin at the interface between the colon and the immune system (11). Given the evidence for altered immunogenic intestinal flora in frail older adults, and the decreasing barrier function of the aging intestinal epithelium, and the known anti-inflammatory functions of lactoferrin, the use of oral lactoferrin for CI suppression in older adults is highly biologically plausible. (13-15;65-68). Beyond this mechanistic rationale, oral lactoferrin has demonstrated to safely and significantly reduce the incidence of neonatal sepsis in prior studies (69) and post-antibiotic diarrhea in older nursing facility residents (70). In older adults, lactoferrin was well tolerated in late stage cancer patients and increased overall survival in a study that did not include inflammatory measures (71, 72). A prior study of bovine lactoferrin demonstrated significant reductions of CRP and IL-6 levels in post-menopausal women treated for 6 months with minimal or no side effects (16). Lactoferrin has previously been used as a chronic diarrhea intervention in other vulnerable populations with minimal safety concerns and few if any adverse outcomes related to lactoferrin (70;73,74).

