Based on a two-sided two-sample t-test with a Type I error of 0.05, a sample size of 23 subjects per group (46 in total) will achieve 80% power to detect a difference of 0.86 SD or greater in logIL-6 between the treatment group and the placebo group at the end of the 6-month trial. Secondly, we will compare the linear rate of change in logIL-6 between the treatment and the placebo groups by modeling the individual trajectories of the outcome. With 20 subjects per group, three repeated measurements of IL-6 assessed at baseline, 3, and 6 months, and a correlation of 0.54 between measurements, we will have 80% power to detect a difference of 1.3 SD units (equivalent to a cross-sectional between-group difference of 0.65SD different at 6 months) or greater in the yearly rate of change in logIL-6 between the treatment and the placebo group. The within subject between-measurement correlation of 0.54 was estimated using longitudinal data from the Women's Health and Aging Study II. Therefore, using longitudinal data, we will have adequate power to detect a difference similar to the 0.63 SD (or 2.5 pg/mL) difference observed at the end of a 6-month, randomized clinical study of a ribonuclease-enriched lactoferrin supplement in post-menopausal women (16). Given these calculations, we are aiming to recruit up to 60 individuals, 30 in each group, in order to maximize our ability to detect differences between treatment and placebo groups. This increased number beyond what are calculated here will take into account anticipated drop outs during the treatment period and leave us with an estimated 'complete completer' group of 46 total. In addition, we are estimating that we will need to have at least 250 individuals recruited into the protocol in order to identify those eligible by inflammatory mediator criteria listed above.

8. Risks

Six Minute Walk Test: This is performed by having the participant walk along a straight hallway for six minutes and measuring the distance walked and the sensation of leg fatigue and dyspnea. The participant may stop at any time if they feel uncomfortable. As with any exercise test, there is a theoretical risk that a participant could suffer cardiac risk from arrhythmia or ischemia, or orthopedic risk from falling or stumbling. Risks are minimized by conducting the test in a medically supervised environment with trained personnel.

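### The IL-6 exclusion limit is written in pg/ul and the IL-6 entry threshold in pg/ml, so as written the upper limit is 30,000 pg/ml and cannot operate

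*Combined protocol and SAP*

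**What the plan says.** The two IL-6 limits stand next to each other in Section 5 of the combined protocol and SAP. The inclusion criterion is "serum IL-6 level ≥ 2.5 pg/ml or TNFR1 level ≥ 1500 pg/ml". The exclusion list opens with "Participants with IL-6 levels above 30.0 pg /ul".

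Four other places bear on how these are read:

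- Section 4 (Study Procedures, Baseline Visit) makes eligibility binding: "Individuals meeting eligibility criteria (described below) will be scheduled for a baseline visit".
- Section 4 (Measurements Performed at Visits) makes the same marker an endpoint: "Primary outcome will be serum IL-6 and sTNFR1 as measured by ELISA".
- Section 3 (Background) explains the lower limits. The IL-6 cutoff "point for the study inclusion criteria for IL6 was identified based on a published threshold serum value", and the sTNFR1 cutoff came from a loess curve. It says nothing about an upper limit.
- Section 7 (Study Statistics) gives the only other IL-6 concentration, again in pg/mL: "0.63 SD (or 2.5 pg/mL) difference observed at the end of a 6-month, randomized clinical study".

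**The concern.** Two limits on one serum marker, meant to bracket the eligible range, are in units that differ by a factor of 1,000. Taken literally, the upper one lies so far above the lower one that it sets no working bound.

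What is at stake is the definition of the study population. The Abstract describes the agent under test as "a known anti-inflammatory agent, on reducing low grade CI, mobility limitations, and cognitive decline in older adults", and the exclusion list also removes people whose markers may be raised for other reasons. An upper IL-6 limit fits that purpose, but one that cannot operate does not serve it. Staff, monitors and later readers also cannot tell from the text which rule was applied at screening.

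**Working it through.** The ceiling is a stated limit, not a derived one, so there is no calculation in the plan to reproduce. The check is a unit conversion followed by a plausibility check on the document's own IL-6 scale.

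**Inputs**

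- Exclusion ceiling: 30.0 pg/ul (Section 5).
- Inclusion threshold: 2.5 pg/ml (Section 5).
- IL-6 scale: 2.5 pg/mL set equal to 0.63 SD (Section 7).
- Conversion: 1 ml = 1,000 ul, by definition.

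**Step 1: common unit.** 30.0 pg/ul × 1,000 ul/ml = 30,000 pg/ml.

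**Step 2: ratio to the threshold.**

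| Reading of the ceiling | In pg/ml | Ratio to 2.5 pg/ml |
|---|---|---|
| As written (pg/ul) | 30,000 | 30,000 / 2.5 = 12,000 |
| Same number in pg/ml (comparison only) | 30 | 30 / 2.5 = 12 |

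The two readings differ by 12,000 / 12 = 1,000.

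**Step 3: could the written limit exclude anyone?** The implied SD is 2.5 / 0.63 = 3.97 pg/mL.

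- As written: (30,000 − 2.5) / 3.97 ≈ 7,560 SDs above the threshold.
- Same number in pg/ml: (30 − 2.5) / 3.97 ≈ 6.9 SDs above the threshold.

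The SD is only a rough guide. It comes from a cited study in post-menopausal women, and Section 7 sets SD units beside raw pg/mL in a paragraph that otherwise works in logIL-6. The conclusion does not depend on it: with an SD ten times larger, the written ceiling would still be about 756 SDs above the threshold.

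**Step 4: is it corrected elsewhere?** The three other cytokine values (IL-6 2.5 and TNFR1 1500 in Section 5, the IL-6 difference of 2.5 in Section 7) are all in pg/ml. The pg/ul unit occurs only in the exclusion criterion. The screening procedure in Section 4 describes the test and retest by the lower thresholds alone and mentions no ceiling.

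**The case against.** The best case on the other side is that this is a typing slip with almost no consequence. One laboratory runs the ELISA, so both limits were probably applied in one unit whatever the protocol says. Other safeguards work independently of the ceiling: raised cytokines must be confirmed on a second sample within four weeks, and the exclusion list covers daily anti-inflammatory drugs, severe rheumatoid arthritis, recent hospitalization for infection, and malignancy. The power calculations use logIL-6, which dampens extreme values. The 12,000-fold figure measures a reading that was probably not intended; it is not a measure of harm. And since the documents give no IL-6 distribution for the screened population, any effect on enrolment is inference.

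Most of this stands as to weight. It does not remove the error. A laboratory's habits do not correct a written criterion, and the intended value cannot be recovered from the text. The repeat test guards against a passing rise but not against a persistently very high level. A PDF-reading fault cannot be ruled out without the source page, but it is unlikely, because pg/ml reads correctly in Sections 5 and 7.

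**Conclusion.** The inconsistency is real. As written, the IL-6 ceiling is 30,000 pg/ml, 12,000 times the entry threshold, and it provides no working upper limit. The mismatch and the arithmetic are certain. That practically no one would be excluded is an inference from the Section 7 scale, and a robust one.

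The point is minor. It does not bias the comparison between arms and changes no sample-size figure. The number of participants affected cannot be computed from the documents and may be zero, in particular if the laboratory applied both limits in one unit. Nothing here says which upper limit is the right one.

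**What to change.** Reconcile the inclusion and exclusion criteria in Section 5. The sponsor or investigator should:

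1. confirm the intended upper IL-6 limit and record its source, as Section 3 does for the lower limits;
2. state both IL-6 limits in the unit the laboratory reports;
3. say which sample the ceiling applies to (screening visit, additional blood test, or both), since Section 4 does not;
4. check the stored screening values of everyone already enrolled against the confirmed limit. If a different limit was in use, look also at anyone screened out on high IL-6.

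The cost is a short protocol correction and a look-up of existing values for at most 60 enrolled participants, plus any screen failures on this criterion. No new data are needed.

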For this study, Recombinant Human lactoferrin (rhLF) a partially iron saturated form of lactoferrin in 250 mg capsules and matching placebo capsules will be provided by Ventria Bioscience Biotech company at bulk pricing. Each capsule will contain 250 mg of rhlactoferrin (rhLF) as active ingredient and cellulose, magnesium stearate, and silicon dioxide as inert ingredients. Subjects will receive either 1500 mg of rhlactoferrin in capsule form twice a day or a placebo in exact matching capsules. Dosing will be six 250 mg capsules twice a day based on prior dosing used safely in studies of diarrhea in a nursing home population (70). This treatment will take place for approximately 3 months (87 days). Recombinant human lactoferrin (rhLF) is produced through standard methods of genetic modification and plant transformation. The rice grain in which the protein accumulates is stable and well suited as a production system Recombinant human lactoferrin has been purified from transgenic rice using standard food industry procedures and current good manufacturing practices. Each placebo capsule will contain cellulose, magnesium stearate, and silicon dioxide, manufactured in full compliance with all pharmaceutical regulation.

7. Study Statistics

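### No planned comparison uses baseline logIL-6 as a covariate; against the unadjusted 6-month t-test, ANCOVA would cut variance by about 27% at r = 0.54 and about 7% at r = 0.3

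*Combined protocol and SAP*

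**What the plan says.** Section 7 (Study Statistics) opens with the sizing: "Based on a two-sided two-sample t-test with a Type I error of 0.05, a sample size of 23 subjects per group" gives 80% power for a difference of 0.86 SD in logIL-6 at 6 months. No covariate is mentioned. The plan will secondly "compare the linear rate of change in logIL-6 between the treatment and the placebo groups by modeling the individual trajectories of the outcome", with "three repeated measurements of IL-6 assessed at baseline, 3, and 6 months". "The within subject between-measurement correlation of 0.54" comes from an external cohort, the Women's Health and Aging Study II. The section then concludes that "using longitudinal data, we will have adequate power to detect a difference similar to the 0.63 SD" seen in an earlier lactoferrin study. It expects 46 completers out of 60 recruited.

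Section 4 (Phlebotomy) states: "Primary outcome will be serum IL-6 and sTNFR1 as measured by ELISA". Blood is drawn at the baseline visit, and Section 7 itself lists a baseline IL-6 value. Section 6 gives a treatment period of about 3 months (87 days). Nowhere is baseline logIL-6 or sTNFR1 named as a covariate, and the form of the trajectory model is not given.

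**The concern.** A two-sample t-test at 6 months discards a measurement that every participant will already have and that the plan itself takes to correlate 0.54 with later values. In a trial with 46 expected completers, and at least 250 people to be recruited to find the eligible ones, that precision is worth having. Adjustment also corrects for chance baseline imbalance, which can be appreciable with 23 per arm.

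The slope comparison does bring baseline in. How much it gains depends on whether each arm has its own intercept or the arms share a baseline mean, and Section 7 does not say. The choice matters because the plan's statement about 0.63 SD rests on this comparison.

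**Working it through.** **Inputs.** From Section 7: 23 completers per arm, two-sided 0.05, sizing effect 0.86 SD, cited effect 0.63 SD, r = 0.54, visits at 0, 3 and 6 months. Assumed here: r = 0.4 and 0.3 as lower values, equal correlation between all visits, equal variances, complete data. Power is from the noncentral t with noncentrality d / √(2v/n), where v is the variance relative to the t-test.

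**1. The plan's own figure.** With v = 1 and 44 df, noncentrality at 0.86 SD is 0.86 / √(2/23) = 2.92, and power is 81.4%. The exact requirement is 22.2, so 23 per arm reproduces. The difference detectable at 80% power is 0.845 SD. At 0.63 SD the noncentrality is 2.14 and power is 55%.

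**2. ANCOVA on log baseline.** The large-sample variance is 1 − r². Estimating the covariate slope multiplies it by 1 + 1/(2n − 4) = 1 + 1/42 = 1.024. With 43 df:
- r = 0.54: (1 − 0.2916) × 1.024 = 0.725, a cut of about 27%
- r = 0.4: 0.84 × 1.024 = 0.860, a cut of about 14%
- r = 0.3: 0.91 × 1.024 = 0.932, a cut of about 7%

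Simulation with 200,000 trials per setting gives ANCOVA power at 0.63 SD of 69.0%, 61.4% and 58.0%, in agreement. Break-even with the t-test is where (1 − r²) × 1.024 = 1, which is r of about 0.15.

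**3. Slope comparison, free intercept per arm.** With three equally spaced visits the least-squares weights are proportional to −1, 0, +1. The fitted 6-month change is therefore the 6-month value minus baseline, with v = 2(1 − r): 0.92, 1.20 and 1.40. It beats the t-test only when r exceeds 0.5.

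**4. Slope comparison, common baseline mean.** Generalised least squares gives v = 0.691, 0.800 and 0.845, if the difference grows linearly to month 6. These are large-sample values, so the like-for-like ANCOVA values are 0.708, 0.840 and 0.910.

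**5. Common baseline mean, visit as a category.** For the 6-month contrast, v = 0.708, 0.840 and 0.910, the same as large-sample ANCOVA, with no linearity assumption.

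| 23 per arm | Detectable at 80% power: r = 0.54 / 0.4 / 0.3 | Power at 0.63 SD: r = 0.54 / 0.4 / 0.3 |
|---|---|---|
| Unadjusted t-test | 0.845 SD throughout | 55% throughout |
| ANCOVA, with covariate cost | 0.72 / 0.78 / 0.82 SD | 69 / 61 / 58% |
| Slope, free intercepts | 0.81 / 0.93 / 1.00 SD | 59 / 48 / 42% |
| Slope, common baseline mean (large-sample) | 0.70 / 0.76 / 0.78 SD | 71 / 65 / 62% |

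The slope rows use 23 per arm and 0.63 SD so that they can be compared with the others. Section 7 states slope power for 20 per group and 0.65 SD at 6 months; that statement is not assessed here.

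**The case against.** The strongest reply is that the plan already uses baseline. The slope comparison includes it as the first repeated measure and takes out group differences in starting level. That stands. A reader might infer that the plan ignores baseline altogether, or that the slope comparison helps only with a common baseline mean. The documents support neither: at r = 0.54 even the free-intercept slope has 59% power against 55% for the t-test. With a common baseline mean, which Section 7 does not rule out, little or nothing is lost.

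A reader might also take the 55% as showing that the plan's statement about 0.63 SD is wrong. It does not show this, because the plan rests that statement on the longitudinal comparison; the t-test is sized for 0.86 SD and meets it.

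Next, the t-test appears only in a sizing sentence, and sizing on an unadjusted test is conservative and does not forbid adjustment. This stands in part. The wording that introduces the slope comparison as the second one implies that the t-test is the first, and no other 6-month comparison is named.

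Finally, 0.54 comes from an external cohort, while this trial selects participants on IL-6 or TNFR1 level, so its correlation may be lower. That is fair, and it is why the gain is given as a range. At r = 0.3 it is only about three points of power.

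**Conclusion.** The point holds as a recommended improvement in efficiency. It is not an error of validity, and the sample size of 23 per arm is correctly derived for the test stated. Against that t-test, ANCOVA cuts variance by about 27% at r = 0.54 and about 7% at r = 0.3, and the gain vanishes only below r of about 0.15.

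Against the slope comparison the gain depends on the unstated model. It is substantial if each arm has its own intercept, and roughly nil if the arms share a baseline mean and the difference grows linearly to month 6. That linear growth is itself an assumption, since treatment ends at about month 3.

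The figures rest on equal correlations, equal variances and 23 completers per arm. Section 7 gives no correlation for sTNFR1, so the gain there cannot be quantified.

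**What to change.** - Analyse 6-month logIL-6, and likewise log sTNFR1, by ANCOVA on the log baseline value. Alternatively, use a repeated-measures model with a common baseline mean, visit as a category and treatment-by-visit terms; this can include every randomised participant with any value.
- Report the 6-month contrast, on which the plan is sized, and also the 3-month contrast, near the end of treatment.
- If the slope comparison is kept, state that the arms are constrained to a common baseline mean.
- Keep the unadjusted t-test as a sensitivity analysis.
- Restate the difference detectable with 23 completers per arm as about 0.72 SD at r = 0.54 to 0.82 SD at an assumed r = 0.3.

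The cost is analysis wording and one degree of freedom, with no extra participants, visits or samples.
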